**CLINICAL PROTOCOL**

Date: September 16, 2016	Phase: Phase II Study	Protocol No.: GC-009
-----------------------------	--------------------------	-------------------------

**C. ADDITIONAL PRINCIPLES FOR MEDICAL RESEARCH COMBINED WITH MEDICAL CARE**

1. The physician may combine medical research with medical care, only to the extent that the research is justified by its potential prophylactic, diagnostic or therapeutic value. When medical research is combined with medical care, additional standards apply to protect the patients who are research subjects.
2. The benefits, risks, burdens and effectiveness of a new method should be tested against those of the best current prophylactic, diagnostic, and therapeutic methods. This does not exclude the use of placebo, or no treatment, in studies where no proven prophylactic, diagnostic or therapeutic method exists.
3. At the conclusion of the study, every patient entered into the study should be assured of access to the best proven prophylactic, diagnostic and therapeutic methods identified by the study.
4. The physician should fully inform the patient which aspects of the care are related to the research. The refusal of a patient to participate in a study must never interfere with the patient physician relationship.
5. In the treatment of a patient, where proven prophylactic, diagnostic and therapeutic methods do not exist or have been ineffective, the physician, with informed consent from the patient, must be free to use unproven or new prophylactic, diagnostic and therapeutic measures, if in the physician's judgment it offers hope of saving life, re-establishing health or alleviating suffering. Where possible, these measures should be made the object of research, designed to evaluate their safety and efficacy. In all cases, new information should be recorded and, where appropriate, published. The other relevant guidelines of this Declaration should be followed.

**CLINICAL PROTOCOL**

Date: September 16, 2016	Phase: Phase II Study	Protocol No.: GC-009
-----------------------------	--------------------------	-------------------------

**22. APPENDIX E – GLAUKOS TRAVOPROST INTRAOCULAR IMPLANT SURGICAL INSTRUCTIONS**

Do not use the implant if the Tyvek lid on the blister tray has been opened or the packaging appears damaged. In such cases, the sterility of the implants may be compromised.

**Surgical Instructions**

1. The eye should be anesthetized using general, retrobulbar, peribulbar, or topical anesthesia per standard hospital or ambulatory surgery center procedures.
2. It is recommended that the implant surgery be performed from the temporal side, using a temporal clear corneal incision, to provide clear access for the surgical instruments. The implant will be implanted through the trabecular meshwork on the nasal side.
3. Create a clear corneal incision at the temporal limbus location using an instrument of the surgeon's choice.
4. A cohesive viscoelastic is added to the anterior chamber as needed to improve visualization of the angle, and to maintain IOP for use of the gonioscope.
5. A gonioscope is placed on the cornea and the surgical microscope and the patient are positioned as needed to visualize the angle, through the gonioprism, on the nasal side of the eye. Tilting the patient's head as far as practical away from the surgeon, and also tilting the microscope toward the surgeon will help viewing of the angle.
6. The angle is inspected using a gonioprism to ensure good visualization at the nasal implant location.
7. Remove the G2TR-[ ] or G2TR-[ ] on its inserter from the blister tray. Inspect the implant on the tip of the inserter.
8. When ready for implantation, remove safety clip which holds trigger in place. Keep finger on trigger button to ensure it remains in the forward position and doesn't prematurely release implant.
9. Insertion of Model G2TR-[ ] or G2TR-[ ]
  - a. Deepen the anterior chamber with additional viscoelastic to aid in chamber maintenance as needed.
  - b. Enter the anterior chamber with the implant using supplied inserter.
  - c. Advance to the pupillary margin before replacing the goniolens onto the eye.
  - d. Care must be taken to avoid contact with the lens or cornea.
  - e. Advance to the anterior chamber angle and approach the trabecular meshwork.
  - f. Press the distal end of the implant directly into and through trabecular meshwork until the barb at the tip securely penetrates the sclera at the outer wall of Schlemm's canal, and the base of the cylindrical

**CLINICAL PROTOCOL**

Date: September 16, 2016	Phase: Phase II Study	Protocol No.: GC-009
-----------------------------	--------------------------	-------------------------

reservoir is firmly in contact with and compressing the trabecular meshwork.

- g. During scleral penetration, it may be necessary to apply firm and focused responsive pressure against the sclera on the outside of the eye to react against the penetration and keep the tissue from collapsing around the sharp tip of the implant thereby preventing penetration.
- h. Once the tip barb of the implant is securely embedded in sclera, carefully slide the trigger button rearward to open the jaws of the gripper and thus release the implant from the inserter. Back the inserter away from the implant without allowing it to pull the implant of position.
- i. Withdraw the insertion instrument from the eye.

10. High-magnification examination is performed to confirm that the implant is in proper position (i.e., the proximal end rests in the anterior chamber with an unobstructed membrane) and securely attached with the tip barb thoroughly embedded in sclera.

11. It is normal for an edge of the implant to make contact with iris, but most of the membrane should be unobstructed by iris.

12. The anterior chamber is irrigated and aspirated with balanced salt solution (BSS) through the corneal wound to remove all viscoelastic. The surgeon may press down on the posterior edge of the incision as needed to facilitate complete removal of viscoelastic.

13. The anterior chamber is inflated with saline solution as needed to achieve physiologic pressure.

Do not use the implant if the Tyvek lid on the blister tray has been opened or the packaging appears damaged. In such cases, the sterility of the implants may be compromised.

**CLINICAL PROTOCOL**

[figure not shown]
[figure not shown]
Date: September 16, 2016	Phase: Phase II Study	Protocol No.: GC-009
-----------------------------	--------------------------	-------------------------

**CLINICAL PROTOCOL**

Date: September 16, 2016	Phase: Phase II Study	Protocol No.: GC-009
-----------------------------	--------------------------	-------------------------

**CLINICAL PROTOCOL**

Date: September 16, 2016	Phase: Phase II Study	Protocol No.: GC-009
-----------------------------	--------------------------	-------------------------

**CLINICAL PROTOCOL**

[figure not shown]
Date: September 16, 2016	Phase: Phase II Study	Protocol No.: GC-009
-----------------------------	--------------------------	-------------------------

**CLINICAL PROTOCOL**

Date: September 16, 2016	Phase: Phase II Study	Protocol No.: GC-009
-----------------------------	--------------------------	-------------------------

[figure not shown]
[figure not shown]
**CLINICAL PROTOCOL**

Date: September 16, 2016	Phase: Phase II Study	Protocol No.: GC-009
-----------------------------	--------------------------	-------------------------

**CLINICAL PROTOCOL**

Date: September 16, 2016	Phase: Phase II Study	Protocol No.: GC-009
-----------------------------	--------------------------	-------------------------

[figure not shown]

[figure not shown]
**CLINICAL PROTOCOL**

Date: September 16, 2016	Phase: Phase II Study	Protocol No.: GC-009
-----------------------------	--------------------------	-------------------------

**CLINICAL PROTOCOL**

Date: September 16, 2016	Phase: Phase II Study	Protocol No.: GC-009
-----------------------------	--------------------------	-------------------------

**CLINICAL PROTOCOL**

Date: September 16, 2016	Phase: Phase II Study	Protocol No.: GC-009
-----------------------------	--------------------------	-------------------------

**24. APPENDIX G – ARTIFICIAL TEARS PACKAGE INSERT**

**CLINICAL PROTOCOL**

[figure not shown]
Date: September 16, 2016	Phase: Phase II Study	Protocol No.: GC-009
------------------------------------	---------------------------------	--------------------------------

col No.:  
09

**CLINICAL PROTOCOL**

Date: September 16, 2016	Phase: Phase II Study	Protocol No.: GC-009
------------------------------------	---------------------------------	--------------------------------

**CLINICAL PROTOCOL**

Date: September 16, 2016	Phase: Phase II Study	Protocol No.: GC-009
-----------------------------	--------------------------	-------------------------

**25. APPENDIX H – ASSIGNING SUBJECT NUMBERS AND KITS**

Subject and kit numbers will be dispensed using in accordance with detailed instructions provided separately. The investigator or his/her designee must access the electronic data base to obtain details of subject randomization and kit use.

## CLINICAL PROTOCOL

Date:	Phase:	Protocol No.:
September 16, 2016	Phase II Study	GC-009

## 26. APPENDIX I - PROCEDURES FOR EXAMINATIONS

**CLINICAL PROTOCOL**

Date: September 16, 2016	Phase: Phase II Study	Protocol No.: GC-009
-----------------------------	--------------------------	-------------------------

[figure not shown]

**26.4. Gonioscopy**

Gonioscopy will be used to assess angle abnormalities including presence of goniosynechiae, angle anatomy and implant location (in subjects with implants). At the screening exam, the Shaffer system for grading the angle anatomy will be used as follows:

[figure not shown]

**NOTE:** Gonioscopy is to be performed at all exams starting at Day 1 postoperative

[figure not shown]
**26.5. Slit-lamp Biomicroscopy**

The slit lamp exam will include the measurement of aqueous cell and flare by a standard grading system and an evaluation for the presence of corneal abnormalities, pupillary irregularities, iris atrophy and pigment dispersion. Crystalline lens status (for phakic subjects) will also be assessed.

[figure not shown]

**CLINICAL PROTOCOL**

Date: September 16, 2016	Phase: Phase II Study	Protocol No.: GC-009
-----------------------------	--------------------------	-------------------------

**General Instructions**

**26.6. Intraocular Pressure (IOP)**

Applanation Tonometry using a Goldmann tonometer will be used to measure intraocular pressure at all visits except for the operative visit. At each visit, IOP will be measured prior to gonioscopy or dilation of the pupil.

**CLINICAL PROTOCOL**

Date: September 16, 2016	Phase: Phase II Study	Protocol No.: GC-009
-----------------------------	--------------------------	-------------------------

**26.6.1. Standard IOP Measurement**

Standard postoperative IOP measurements will be taken at 8:00 am ( $\pm$  30 minutes).

**26.6.2. Diurnal IOP Measurement**

Diurnal IOP measurements will be taken at 8:00 am  $\pm$ 30 minutes, 10:00 am  $\pm$ 30 minutes, and 4:00 pm  $\pm$ 30 minutes).

**26.7. Ophthalmoscopy**

Ophthalmoscopy will be performed with pupil dilation to examine the fundus and nerve abnormality(ies). The dilated fundus exam will include evaluation of the macula and vessels as well as peripheral fundus examination.

The cup-to-disc (C/D) ratio is a numerical expression indicating the percentage of disc occupied by the optic cup. Vertical C/D ratio will be assessed, and a score from 0.1 to 0.9 [REDACTED] will be recorded.

**26.8. Visual Field**

Visual fields must be automated threshold visual fields using [REDACTED] This program will be used for the duration of the study when required. Visual field testing can be performed dilated or undilated as long as the method is

**CLINICAL PROTOCOL**

Date: September 16, 2016	Phase: Phase II Study	Protocol No.: GC-009
-----------------------------	--------------------------	-------------------------

consistent for each subject at each visit. There are no restrictions on how to prepare subject's eyes for the visual field exam. NOTE: Visual field exams conducted  $\leq 6$  months of the screening visit can be used as part of the subject's evaluation for inclusion in (or exclusion from) the study as long as the test is performed with [REDACTED] Values for mean deviation and pattern standard deviation will be recorded.

**26.9. Specular Microscopy**

Specular microscopy will be performed in all subjects in both groups. [REDACTED]

[REDACTED] Endothelial cell

density, percent hexagonality and the coefficient of variation will be assessed from calibrated specular microscope images.

[REDACTED]  
[REDACTED]  
[REDACTED]  
[REDACTED]  
[REDACTED]  
[REDACTED]  
[REDACTED]  
[REDACTED]

## CLINICAL PROTOCOL

Date:	Phase:	Protocol No.:
September 16, 2016	Phase II Study	GC-009

The image consists of a series of horizontal black bars on a white background. The bars are of varying lengths and are positioned at different heights. Some bars are longer and extend across more of the frame, while others are shorter and located higher up. The overall effect is abstract and digital, resembling a bar chart or a data visualization.

## 26.10. Conjunctival Hyperemia, Iris, Eyelash and Periorbital Assessments and Photographs and Blood Sampling

At the examinations specified in Section 7.3 and Appendix A, the site staff will perform conjunctival hyperemia, periorbital, iris and eyelash assessments at any time during the visit.

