**Masking:**

- Observer-masked (IOP readings, assessments of symptomatology)
- Subject-masked

---

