**Screening Phase**

The screening phase will consist of Visit 1 (Screening), a washout/waiting period, and Visit 2 (Baseline). At the Screening visit, prospective subjects will be evaluated to determine if they meet the screening criteria. Subjects who qualify for screening will undergo a washout of any current topical IOP-lowering medication in the designated study eye according to the following schedule:

Subjects who have not used topical ocular hypotensive medications within [REDACTED] weeks prior to the Screening visit must wait at least [REDACTED] days before being scheduled for the Baseline visit.

Following the required washout/waiting period, subjects will return for the Baseline visit, and IOP will be measured at 8:00 am, 10:00 am and 4:00 pm. To qualify for the study, subjects must have, at the Baseline exam, mean diurnal IOP between [REDACTED] and [REDACTED] in the study eye; and they must meet all other entry criteria. Qualified subjects will be scheduled for treatment.

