### 7.1.6. Ophthalmoscopy

Ophthalmoscopy will be performed with pupil dilation to examine the fundus and nerve abnormalities for the study eye at Screening, Weeks 4, 6, Months 3, 6, 9, 12, 15, 18, 21, 24, 27, 30, 33, and 36. The dilated fundus exam will include evaluation of the macula and vessels as well as peripheral fundus examination.

In addition, the number and percentage of subjects with any clinically significant findings at any post-baseline visits, and at each scheduled post-baseline visit will be also presented by treatment group.

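### Protocol 26.10 lets hyperemia be scored at any point in the visit, before or after eye procedures that differ between Baseline and follow-up, and no visible text says who scores it

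*Protocol*

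**What the plan says.** On timing, Protocol Appendix I, 26.10 has site staff "perform conjunctival hyperemia, periorbital, iris and eyelash assessments at any time during the visit". The only ordering rule visible in the appendix is in 26.6: "At each visit, IOP will be measured prior to gonioscopy or dilation of the pupil". It does not place hyperemia.

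On procedures, 26.4 states that "Gonioscopy is to be performed at all exams starting at Day 1 postoperative", and that the examination covers "angle anatomy and implant location (in subjects with implants". SAP 7.1.6 schedules dilated ophthalmoscopy "for the study eye at Screening, Weeks 4, 6, Months 3, 6, 9, 12, 15, 18, 21, 24, 27, 30, 33, and 36". SAP 7.1.11 has hyperemia assessed at Baseline and at each scheduled visit from Week 4, with the grades tabulated once from CRF data and once from Central Reading Center data.

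On masking, the Protocol Summary reads "Observer-masked (IOP readings, assessments of symptomatology". SAP 2.2 describes masking of the IOP observer and the subject. Protocol Section 11 refers to staff who make certain measurements, and its detail is not visible.

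On use, Protocol 5.2 and 9.5.2 plan change from baseline in hyperemia. Protocol 9.6.5 plans no formal testing of safety outcomes.

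**The concern.** The Protocol's Introduction names ocular hyperemia among the side effects of prostaglandin analogues, and one of the two clinical hypotheses is that the implants are well tolerated. With no formal safety tests, the tabulated grades are the evidence on this effect.

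Contact with the eye and drops given at a visit can change how red the eye looks. That premise is general clinical knowledge; the documents do not state it. The protocol protects IOP by placing it ahead of gonioscopy and dilation, but leaves hyperemia free to fall anywhere. If the procedures that may precede scoring differ between Baseline and follow-up, part of a change from baseline can come from the visit routine and not from treatment.

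A second question concerns the person. Whoever does gonioscopy can tell an implanted eye from a sham eye. If that person also scores redness, the score is given with knowledge of the treatment.

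**Working it through.** The visible text gives no hyperemia rate, effect size or precision target, so there is no plan figure to reproduce. The check sets the passages side by side, then adds one illustration on assumed inputs.

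**1. Visits with a hyperemia score.** SAP 7.1.11 gives Baseline and every scheduled visit from Week 4. By the visit list in SAP 2.2, follow-up is Week 4, Week 6, Month 3 and then every 3 months from Month 6 to Month 36: 3 + 11 = 14 visits.

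**2. Procedures listed at those visits** (Protocol 4.1 and 26.4; SAP 7.1.6):

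| Visit | Tonometry readings | Gonioscopy | Dilated ophthalmoscopy |
|---|---|---|---|
| Baseline | 3 | not listed | not listed |
| Week 4 | 1 | yes | yes |
| Week 6, Month 3 | 3 | yes | yes |
| Months 6 to 36 | 1 | yes | yes |

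The three Baseline readings are from Protocol 4.1: "IOP will be measured at 8:00 am, 10:00 am and 4:00 pm". For gonioscopy and the dilated fundus examination, Protocol 9.6.3 and SAP 7.1.6 name Screening as the pre-treatment visit. All 14 dates in SAP 7.1.6 after Screening coincide with hyperemia visits.

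**3. What 26.10 permits.** At Baseline, a score may follow none to three tonometry readings. At follow-up, it may also follow gonioscopy and dilation. The visible lists are the same for all three arms.

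**4. Illustration (all inputs assumed).** Take a four-level grade distribution of 0.60/0.30/0.08/0.02 in every arm, with no true change over time. Let procedures before scoring move a fraction q of eyes up one grade. Then:

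P(moderate or worse) = 0.08 + 0.02 + q × 0.30

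- q = 0: 10%
- q = 0.2: 10% + 6% = 16%
- q = 0.4: 10% + 12% = 22%
- q = 0.6: 10% + 18% = 28%

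If Baseline is scored undisturbed and follow-up after procedures, every arm shows a spurious rise of 6, 12 or 18 points, and the difference between arms is 0. If Baseline is scored after tonometry with q = 0.2 and follow-up is scored first, every arm shows a spurious fall of 6 points. Even the sign depends on site habit, which the rule leaves open.

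**5. Who scores.** Gonioscopy takes place at Day 1-2 and Day 10, before the first post-treatment hyperemia score at Week 4. Someone who did it then has already seen whether there is an implant. Moving the score to the start of a later visit does not re-mask that person. This is a question of who scores, not when.

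**The case against.** Much of the relevant text is redacted: the visit steps in Protocol 7.3, Appendix A, the scoring method in 26.10.1 and the masking detail in Section 11. An order or a named assessor could be stated there. This stands as a limit on the second question. It does not remove the first, because 26.10 states the timing itself. If 7.3 did fix an order, the two would conflict and need to be reconciled.

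It is also fair to say that the procedures are the same by arm, that hyperemia is descriptive, and that the Central Reading Center provides a source apart from the site scorer. All three points stand. The last answers the scorer's knowledge better than it answers redness: a photograph taken after procedures still shows their effect, and neither photograph timing nor reader masking is visible.

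Three stronger readings are tempting, and the documents do not support them.

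- A reader might infer that a masked outcome is contaminated. No visible passage names hyperemia as a masked measure, and the rule permits late scoring without showing that it happens.
- A reader might infer a bias between arms because gonioscopy looks for the implant. Nothing says that it takes longer or causes more redness in implanted eyes.
- A reader might infer that added redness hides a true difference. Suppose the control arm has the distribution above and the implant arm 0.40/0.35/0.18/0.07, so that the implant rate is 25% + q × 35%. For q = 0, 0.2, 0.4 and 0.6 the pairs are 10/25, 16/32, 22/39 and 28/46%. The ratio falls from 2.5 to 2.0, 1.8 and 1.6, but the difference rises from 15 to 16, 17 and 18 points. SAP 7.1.11 reports percentages by grade, not ratios.

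**Conclusion.** The point holds as a minor weakness in measurement. The protocol expressly permits hyperemia to be scored before or after procedures that can alter redness, and the visible schedule has more of these procedures at follow-up than at Baseline. That can add noise and distort change from baseline in all arms. The documents do not give the size or direction, and they show no difference between arms. The range of 6 to 18 points is only an illustration.

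Separately, the visible text does not establish that the scorer is masked or is someone other than the gonioscopist.

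Both conclusions assume that the redacted visit steps say nothing further. The first also assumes that Baseline has no gonioscopy or dilated examination beyond what is listed. The primary IOP analysis is not affected.

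**What to change.** **Protocol 26.10.** State that at every visit where hyperemia is assessed, including Baseline, scoring and photographs come before any drop given at the visit, tonometry, gonioscopy or dilation. Have the existing masked IOP observer score where possible, and in no case the person who does gonioscopy or the implant assessment. The other external assessments can follow later in the visit.

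**SAP 7.1.11, for data already collected.** Name the Central Reading Center grade as the main hyperemia result and the CRF score as supportive. Report photograph timing relative to tonometry, gonioscopy and dilation where it was recorded.

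**Cost.** This reorders existing steps and adds a sentence or two to the SAP, with no new procedure. The downside is a few minutes before the 8:00 am pressure reading, which must stay within the 30 minutes either side allowed by 26.6.1 and 26.6.2. This matters most at Week 6 and Month 3, where the 8:00 am reading is one of the nine primary timepoints. Sites would need to start slightly earlier on those days.

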**CLINICAL PROTOCOL**

Date: September 16, 2016	Phase: Phase II Study	Protocol No.: GC-009
-----------------------------	--------------------------	-------------------------

**26.10.1. Conjunctival Hyperemia**  
Conjunctival hyperemia will be scored

[REDACTED]

**26.10.2. Iris (Color) Assessment**  
Iris pigmentation will be evaluated by

[REDACTED]

